7.3.2.2. Imputation Methods

Observed cases, without imputation, will be used for of analyses.

If the relationship of an AE is missing, it will be considered treatment-related. Missing AE severity will be coded as severe.

7.3.3. Handling of Early Termination Visit Information

If a subject is terminated early from this study the early termination visit data will be analyzed at the closest scheduled visit. If the closest visit has valid data, the early termination data will be assigned to the next available visit.

7.3.4. Pooling of Study Centers

No pooling of study centers is planned for this study.

7.3.5. Coding Conventions for Events and Medications

All adverse events, and medical history will be mapped to the Medical Dictionary for Regulatory Activities (MedDRA Version 20.1) system for reporting (preferred term and body system). Prior and concomitant medications will be coded using WHO-DD (Drug Dictionary) (Version September 2017).

7.3.6. Analysis Software

[figure not shown]
Data manipulation, tabulation of descriptive statistics, calculation of inferential statistics, and graphical representations will be performed primarily using SAS (release 9.4 or higher) for Windows. If the use of other software is warranted, the final clinical study report will detail what software was used and for what purposes.

7.3.7. Study Data

All study data will be formulated into regulatory compliant data sets to provide transparency, traceability, and integrity of trial analysis results from the collection source. Observed study data will be mapped to the CDISC Study Data Tabulation Model (SDTM) and serve as the source data from the trial. All study analyses will be completed using analysis data sets that are derived from the SDTM and follow the CDISC Analysis Data Model (ADaM) architecture. All planned analyses will be performed using the ADaM data sets developed for this study.

The methods for programming the CDISC SDTM and ADaM data sets are described in [Figure 3](#).

Figure 3 SDTM, ADaM, and TFL Development and Validation

Where:

1. Development, Validation, and Maintenance of SDTM Domains
2. Development and Validation of Analysis Data Sets (ADaM), with input source the appropriate SDTM domains.
3. Development and Validation of Tables, Figures, and Listings (TFL), with input data source the analysis specific ADaM data sets.

7.4. Planned Study Analyses

7.4.1. Statistical Summaries: Descriptive and Inferential

No statistical tests will be performed in this study.

Descriptive summaries of variables will be provided where appropriate. For continuous variables, the number of non-missing values (n) and the median, mean, standard deviation, minimum, and maximum will be tabulated. For categorical variables, the counts and proportions of each value will be tabulated. Expansion of descriptive table categories may occur if such elaborations are thought to be useful.

For the summary statistics of all numerical variables unless otherwise specified, minimum and maximum will be displayed to the same level of precision as reported. Mean and median will be displayed to one level of precision greater than the data collected. The standard deviation / standard error will be displayed to two levels of precision greater than the data collected.

Change from baseline scores will be calculated as the post-baseline measurement minus the baseline value.

Unless otherwise specified, all tables will be presented by Modal Dose of 40 mg, 60 mg, 80 mg, and Overall group.

All collected data will be presented in listings. Data not subject to analysis according to this plan will not appear in any tables or figures but will be included in the data listings.

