7 STUDY TREATMENTS

7.1 Treatments Administered

All subjects will begin treatment with AERT at 40 mg per day (2 x 20 mg) for 3 days, then increase to 60 mg per day (3 x 20 mg) for 3 days, and then increase to 80 mg per day (4 x 20 mg). Once the subject has reached the maintenance dose, they will remain on that dose for approximately 1 year (Figure 2). The maintenance dose will be the highest tolerated dose, not exceeding 80 mg per day. The description of study drug kits and treatments is shown below in Table 2. Subjects may choose to taper study drug after Visit 3 if they experience adverse events. Direct consultation with the investigator site must be conducted before consideration for dose taper. Dose tapers should occur over the course of 9 days in 20 mg increments. Subjects should be encouraged to titrate back to 80 mg once adverse events subside or remain on the maximally tolerated AERT dose. Up to 3 dose tapers over the course of the clinical study are permitted.

Table 2: Study Drug Kits and Treatments, Study OS440-3005

Dosage form description:	Blue, round biconvex tablets.
Package description:	HDPE white bottles with 60 active 20-mg tablets.
Daily dose:	40, 60, and 80 mg arbaclofen depending on the study day. There will be a 9-day titration period (3 days at 40 mg/day, 3 days at 60 mg/day, and then increase to 80 mg/day), then an approximately 1-year maintenance period at 80 mg/day or the highest tolerated dose, followed by a 2-week taper period. Study tablets will be taken twice daily (BID).
Cumulative maximal dosage:	up to 28,420 mg arbaclofen
Manufacturer:	Osmotica Pharmaceutical US LLC, Marietta, GA 30062

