7.5 Selection and Timing of Doses in the Study

There will be a 9-day titration period (3 days at 40 mg/day, 3 days at 60 mg/day, and 3 days at 80 mg/day), then a 1-year maintenance period, followed by a 2-week taper period. The maintenance dose will be the highest tolerated dose, not exceeding 80 mg per day. Subjects who discontinue early should also follow the 2-week taper period. Figure 2 presents the dosing regimen flowchart, including titration and taper, to be used during the study.

Figure 2: Flowchart of Open-Label Dosing Regimen, Study OS440-3005

At the end of treatment, a 2-week taper period will take place from Weeks 54 to 56. Subjects who discontinue early should also follow the 2-week taper period.

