8.6. Treatment Compliance

The total number of days at each unique dose level and overall will be summarized.

Dosing information, including date of administration, and days at each unique dose level will be listed by subject.

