10. SAFETY ANALYSES

10.1. Adverse Events

The number and percent of subjects with any treatment-emergent adverse events (TEAEs) will be displayed by system organ class and preferred term (MedDRA Version 20.1). Within each preferred term, subjects will be counted only once if they had more than one event reported during the treatment period.

TEAEs will also be summarized by greatest reported severity for each event preferred term. Counts indicate subjects reporting one or more TEAEs that map to the severity grade classification for each preferred term. At each level of summarization (system organ class or event preferred term) subjects are only counted once and the worst severity case of repeated instances of the same TEAE will be used in tabulations. TEAEs will also be summarized by strongest investigator assessment of relationship to study drug in a similar manner.

In addition to the above described analyses, specific AE summaries will be presented under the following conditions:

- TEAEs by SOC/PT will be presented by modal dose within period (titration/dose response, maintenance, and taper period).

- TEAEs by SOC/PT will be presented by dose the subject was on at time of event within period (titration/dose response, maintenance, and taper period).
- All AE summaries will be presented by dose the subject was on at time of event.

Analyses of AEs will be performed for those events that are considered treatment emergent, where treatment emergent is defined as any AE with onset or worsening on or after the first dose of study drug up until last dose of study drug.

Treatment emergent summarization will be characterized by serious or not, the severity and the relationship with the study drug. A conservative approach will be taken to assess the relationship of an AE to study drug; if the relationship of an event is missing, it will be considered treatment-related. Missing severity will be coded as severe.

All TEAEs will be listed individually by subject. In addition, a separate listing will be produced for AEs that are not treatment-emergent.

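### Default modal-dose columns place some subjects who do not tolerate 80 mg, and their laboratory, vital-sign, USP and disposition data, under a lower dose, and only AEs have a display by actual dose

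*SAP*

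**What the plan says.** SAP 7.4.1 sets the default layout: "Unless otherwise specified, all tables will be presented by Modal Dose of 40 mg, 60 mg, 80 mg, and Overall group". The SAP does not say over what period the mode is taken, whether titration and taper days count, or how ties are resolved. The revision history records a change from two modal-dose categories to three but adds no definition.

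For adverse events, SAP 10.1 adds three displays. The first keeps modal dose as the grouping: "TEAEs by SOC/PT will be presented by modal dose within period (titration/dose response, maintenance, and taper period"). The second has the same breakdown by period but groups each event by the dose actually being taken when it occurred. The third extends that grouping to every AE table: "All AE summaries will be presented by dose the subject was on at time of event".

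SAP 8.6 adds exposure: "The total number of days at each unique dose level and overall will be summarized". SAP 8.1 (disposition), 10.3 (laboratory), 10.4 (vital signs) and 10.6 (USP, ECG) name no other grouping, so the default applies to them.

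On dosing, Protocol 7.5 says: "There will be a 9-day titration period (3 days at 40 mg/day, 3 days at 60 mg/day, and 3 days at 80 mg/day"). Protocol 7.1 says: "The maintenance dose will be the highest tolerated dose, not exceeding 80 mg per day", and on reductions: "Subjects may choose to taper study drug after Visit 3 if they experience adverse events". Section 7.1 also encourages a return to 80 mg once events subside. Section 7.4 limits tapers from 80 mg to three and requires discontinuation if tolerability problems persist.

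**The concern.** The stated purpose of the study (Protocol 11.3, SAP 6) is long-term safety and tolerability data at 80 mg/day, so readers will look first at the 80 mg column. Because the maintenance dose is whatever the subject tolerates, modal dose is partly an outcome of treatment. Grouping by it sorts subjects on how well they did. Those who could not stay on 80 mg may be counted under 40 or 60 mg, and take with them the results recorded while they were on 80 mg.

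For adverse events the dose-at-event tables correct this. For laboratory values, vital signs, USP and disposition nothing does. USP matters most here, because Protocol 9.6.2 includes it to monitor a possible bladder risk of the drug.

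**Working it through.** **Inputs.** Titration is 3 days each at 40, 60 and 80 mg (Protocol 7.5), so 80 mg starts on Day 7. Treatment before the final taper ends at Week 54, which is Day 54 × 7 = 378 (Table 1). Visit 3 is Week 14, Day 98. Assumptions: the modal dose is the one with the most days, there is a single step-down with no return to 80 mg, and the taper is 7 days at 60 mg and 7 at 40 mg where it is counted (Figure 2 is not shown).

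**Plan's own figure.** 3 + 3 + 3 = 9 days, as stated.

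**Stopping from 80 mg after k days there.**

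| Taper days | Days at 40 / 60 / 80 mg | 80 mg is not a mode | Three-way tie | 80 mg is the only mode |
|---|---|---|---|---|
| Not counted | 3 / 3 / k | k ≤ 2 | k = 3 | k ≥ 4 |
| Counted (7+7 assumed) | 10 / 10 / k | k ≤ 9 | k = 10 | k ≥ 11 |

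Where 80 mg is not a mode, 40 and 60 mg tie, and the SAP does not say which column applies.

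**Permanent step-down to 60 mg after Day x.** Days at 80 mg = x − 6. Days at 60 mg = 3 + (378 − x). Setting them equal gives 2x = 387, so x = 193.5.
- x = 193: 187 days at 80 mg, 188 at 60 mg; the mode is 60 mg.
- x = 98 (Week 14): 98 − 6 = 92 days at 80 mg, 3 + 280 = 283 at 60 mg; the mode is 60 mg.
- No step-down: 378 − 6 = 372 days at 80 mg; the mode is 80 mg.

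**What is misplaced.** For the Week 14 step-down, Table 1 has laboratory tests at Weeks 6 and 14, and vital signs and USP at Weeks 2, 6 and 14. All were taken on 80 mg and all are tabulated under 60 mg. ECG, TNmAS-MAL and EDSS are hardly affected. After baseline they fall only at Week 28 (Day 196) and Week 60. A subject who changes column has stepped down by Day 193, so is already on 60 mg at Week 28 apart from a few days of visit window. Week 60 is four weeks after the taper ends.

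**Titration table by modal dose.** If the mode is computed within the period, a completed titration is 3 = 3 = 3, a three-way tie. If it is the whole-study mode, a Day 2 event at 40 mg appears under 80 mg for anyone later maintained there.

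**Does a definition alone help?** With maintenance days only, days at 80 mg = x − 9 and days at 60 mg = 378 − x, which are equal again at x = 193.5. The shift remains.

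**Illustration of size (assumed rates, not in the documents).** Suppose all subjects reach 80 mg, a share f has a given finding at 80 mg and steps down early, and a share p of the others has that finding at 80 mg. The modal 80 mg column shows p. The true share among all who reached 80 mg is f + (1 − f)p. The gap is f(1 − p): 0.10 × 0.60 = 6 points at f = 10%, p = 40%, and 0.40 × 0.80 = 32 points at f = 40%, p = 20%.

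**The case against.** The strongest reply is that tolerability is read mainly from adverse events, and SAP 10.1 already shows every AE summary by dose at the time of the event, also within titration, maintenance and taper. That covers serious events and events leading to discontinuation. There are also an Overall column, days at each dose, and full listings. This stands: a reader might infer that the plan hides the 80 mg adverse-event profile, and it does not. It leaves the laboratory, vital-sign, USP and disposition tables unanswered, because an Overall column and listings cannot isolate 80 mg.

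A reader might also infer that everyone who fails 80 mg changes column. The arithmetic does not support that. Subjects who stop after 4 or more days at 80 mg (11 or more with the assumed taper), who step down after about Day 193, or who return to 80 mg for long enough, stay under 80 mg.

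Nor is the exposed window clearly half of treatment. Protocol 7.1 places reductions for adverse events after Visit 3. On that text the window is about Day 98 to Day 193, 95 of 378 days or about 25%. Section 7.1.1 does not repeat the limit, so the window is uncertain.

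Finally, it is too strong to say that modal dose has no value for titration. That holds only if the mode is computed within the period, and the dose-at-event table for titration is already planned.

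**Conclusion.** The point holds for laboratory, vital-sign, USP and disposition tables. Followed as written, the plan puts some 80 mg data under a lower dose, for subjects selected by not tolerating 80 mg. The tendency is to flatter 80 mg in those tables. The size cannot be stated, because the documents give no step-down or re-titration rates; the 6 to 32 points above only illustrate the mechanism under assumed rates.

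The thresholds (4 or 11 days at 80 mg; about Day 193) rest on a mode taken over the whole study, one permanent step-down to 60 mg, treatment to Day 378 and, for the 11 days, the assumed taper split. The missing window and tie rule are a separate, certain gap: two programmers could build different tables from the same text.

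**What to change.** 1. In SAP 10.3, 10.4 and 10.6, add laboratory, vital-sign and USP summaries by the dose the subject was on at the visit, with Week 60 shown separately as off drug.
2. In SAP 8.1, add disposition and reasons for discontinuation by highest daily dose reached (or by ever having reached 80 mg).
3. In SAP 10.1, use dose at time of event instead of modal dose for the titration and taper periods.
4. In SAP 7.4.1, state the window for modal dose, whether titration and taper days count, and the tie rule. This makes the tables reproducible but does not by itself remove the column shift.

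Protocol 7.1 (reductions over 9 days) and 7.1.1 (20 mg per week) differ on the pace of a step-down, and the passages must be reconciled so that days at each dose are derived in one way.

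The cost is SAP wording and a few more tables. SAP 8.6 already calls for days at each dose, so no new data are needed.

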7.4.2. Interim Analyses and Data Monitoring

No formal interim analysis is planned for this study.

A Data Safety Monitoring Board (DSMB) will oversee study subject safety with respect to AEs and clinically important lab values. DSMB members will be independent of the Sponsor, study sites, and the managing vendors, and will have no other role in the trial. DSMB meetings for Study OS440-3005 will be scheduled after approximately 25% subjects have been randomized or 300 AEs (whichever comes first), 50% subjects have been randomized or 600 AEs (whichever comes first), 75% subjects have been randomized or 900 AEs (whichever comes first) and 100% of subjects have been randomized. The DSMB Chairman will be responsible for determining a time for unscheduled meetings

7.4.3. Multiple Testing Procedures

Not applicable.

8. SUMMARY OF STUDY DATA

8.1. Subject Disposition

A summary of the analysis sets includes the number and percentage of subjects screened (rollover and de novo) and in the safety population. All percentages will be based on the number of subjects screened.

End of trial information will also be summarized in this table, including the number of subjects completing the study and the number of subjects who prematurely discontinued the study with reasons for withdrawal. All percentages will be based on the number of subjects screened.

A by-subject data listing of study completion information including the reason for premature study withdrawal, if applicable, will be presented.

8.2. Protocol Deviations

All protocol deviations will be presented in a data listing. A summary table will also be generated based on the classification of protocol deviations.

8.3. Demographics and Baseline Characteristics

Subject demographic data and baseline characteristics will be tabulated and summarized descriptively. Individual subject demographics and baseline characteristics will be provided in listings.

8.4. Medical and Surgical History

Medical and surgical history will be coded using the MedDRA Version 20.1.

Subject medical and surgical history data including specific details will be presented in a listing.

8.5. Prior and Concurrent Medications

The number and percentages of all concomitant medications will be summarized, Anatomical Therapeutic Chemical (ATC) level 4 and PT. The total number of concomitant medications and the number and percentages of subjects with at least 1 concomitant medication will be summarized.

The number and percentages of all prior medications will be summarized similarly to concomitant medications in a separate table.

A concomitant medication is defined as any medication taken on or after the day of first dose of study drug. The prior medications are defined as any medication that starts and ends prior to the first dose of study drug.

8.6. Treatment Compliance

The total number of days at each unique dose level and overall will be summarized.

Dosing information, including date of administration, and days at each unique dose level will be listed by subject.

9. EFFICACY ANALYSES

9.1. Efficacy Endpoints

Efficacy endpoints include the following:

- Patient Global Impression of Change (PGIC)
- Total Numeric-Transformed Modified Ashworth Score – Most Affected Limb (TNmAS-MAL)
- Total Numeric-Transformed Modified Ashworth Score – Total Limbs (TNmAS-TL)
- Expanded Disability Status Scale (EDSS)

9.2. Efficacy Analyses

PGIC categories will be summarized by frequencies and percentages by study visit. PGIC will also be summarized using descriptive statistics by study visit.

TNmAS-MAL, TNmAS-TL, and EDSS will be summarized descriptively by study visit in terms of actual values and change from baseline values. In addition to this change from baseline (from Visit 6/ET in OS440-3004), the change from baseline in Study OS440-3004 will be summarized for TNmAS-MAL and TNmAS-TL.

10. SAFETY ANALYSES

10.1. Adverse Events

The number and percent of subjects with any treatment-emergent adverse events (TEAEs) will be displayed by system organ class and preferred term (MedDRA Version 20.1). Within each preferred term, subjects will be counted only once if they had more than one event reported during the treatment period.

TEAEs will also be summarized by greatest reported severity for each event preferred term. Counts indicate subjects reporting one or more TEAEs that map to the severity grade classification for each preferred term. At each level of summarization (system organ class or event preferred term) subjects are only counted once and the worst severity case of repeated instances of the same TEAE will be used in tabulations. TEAEs will also be summarized by strongest investigator assessment of relationship to study drug in a similar manner.

In addition to the above described analyses, specific AE summaries will be presented under the following conditions:

- TEAEs by SOC/PT will be presented by modal dose within period (titration/dose response, maintenance, and taper period).

- TEAEs by SOC/PT will be presented by dose the subject was on at time of event within period (titration/dose response, maintenance, and taper period).
- All AE summaries will be presented by dose the subject was on at time of event.

Analyses of AEs will be performed for those events that are considered treatment emergent, where treatment emergent is defined as any AE with onset or worsening on or after the first dose of study drug up until last dose of study drug.

Treatment emergent summarization will be characterized by serious or not, the severity and the relationship with the study drug. A conservative approach will be taken to assess the relationship of an AE to study drug; if the relationship of an event is missing, it will be considered treatment-related. Missing severity will be coded as severe.

All TEAEs will be listed individually by subject. In addition, a separate listing will be produced for AEs that are not treatment-emergent.

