3 STUDY OBJECTIVES

3.1 Primary Objective

The primary objective of this study is to evaluate the long-term safety and tolerability of AERT in patients with spasticity due to MS.

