5 STUDY POPULATION

It is anticipated that approximately 50% of subjects randomized into the double-blind study (Study OSS440-3004) may rollover into this open-label study. In addition, United States (US) subjects who did not participate in Study OS440-3004 (i.e., *de novo* subjects) may also enroll into the current study provided that all inclusion and none of the exclusion criteria are met. In total, approximately 300 subjects are to be enrolled in order to achieve treatment of at least 100 subjects for 6 months, and 50 subjects at 80 mg/day for at least 1 year; however, the sponsor reserves the right to end this clinical study after a sufficient number of subjects have enrolled to complete the requirement.

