4. STUDY OBJECTIVES AND ENDPOINTS

4.1. Study Objectives

4.1.1. Primary Objective

The primary objective of this study is to evaluate the long-term safety and tolerability of AERT in subjects with spasticity due to MS.

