5. STUDY METHODS

5.1. General Study Design and Plan

As background for the statistical methods presented below, this section provides an overview of the study design and plan of study execution. The protocol is the definitive reference for all matters discussed in what follows.

This is a multicenter, open-label, long-term extension study to evaluate the safety and tolerability of oral AERT in subjects with spasticity due to MS. Subjects from the double-blind study (Study OS440-3004) may rollover into this open-label extension study, as well as de novo subjects, provided that all inclusion and none of the exclusion criteria are met.

Eligible de novo subjects will undergo an at least 21-day washout period for withdrawal of all medications used for anti-spasticity and/or muscle relaxation prior to enrolling in this open-label study. There will be a 9-day titration period, then a 52-week maintenance period, followed by a 2-week taper period.

[Figure 1](#) presents the timeline diagram for the study. [Figure 2](#) presents the open-label dosing regimen flowchart, including titration and taper doses, to be used during the study. Once the subject has reached the maintenance dose, they will remain on that dose for approximately 1 year. The maintenance dose will be the highest tolerated dose not exceeding 80 arbaclofen mg per day.

The schedule of assessments is presented in [Table 1](#).

Figure 1 **Timeline Diagram**

[figure not shown]
[figure not shown]

Figure 2 Flowchart of Open-Label Dosing Regimen

At the end of treatment, a 2-week taper period will take place from Weeks 54 to 56. Subjects who discontinue early should also follow the 2-week taper period.

Table 1 Schedule of Assessments

Assessment or Procedure	Baseline ¹	Visits							Final Visit ²
Study Visit	(V6 of prior DB Study)	1	2	3	4	5	6	7 (telephone visit)	8
Study Week	0 (±3 days)	2 (±3 days)	6 (±5 days)	14 (±5 days)	28 (±5 days)	42 (±5 days)	54 (±3 days)	56 (±5 days)	60 (±3 days)
Written informed consent	X								
Inclusion and exclusion criteria	X								
Withdrawal anti-spasticity medication	X								
Assign enrollment number	X								
Demography	X								
Medical/surgical history	X								
Physical examination	X								
Height	X								
Weight	X				X				X
Vital signs ³	X	X	X	X	X	X	X	X	X
Hematology/serum chemistry/urinalysis	X		X	X	X	X	X	X	X
Electrocardiogram	X				X				X
Pregnancy test ⁴	X	X	X	X	X	X	X	X	X
C-SSRS	X	X	X	X	X	X	X	X	X
TNmAS-MAL ⁵	X				X				X
EDSS	X				X				X
PGIC ⁶	X				X				X

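### The adverse-event tables leave the 52-week maintenance period as one block and state no at-risk denominator, so they cannot show how risk changes with time on drug

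*SAP*

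**What the plan says.** Protocol 3.1 sets the primary objective: to "evaluate the long-term safety and tolerability of AERT in patients with spasticity due to MS". SAP 4.1.1 repeats it.

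SAP 5.1 gives the time frame: "There will be a 9-day titration period, then a 52-week maintenance period, followed by a 2-week taper period".

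SAP 10.1 defines the main AE result: "The number and percent of subjects with any treatment-emergent adverse events (TEAEs) will be displayed by system organ class and preferred term". The counting rule is: "Within each preferred term, subjects will be counted only once if they had more than one event reported during the treatment period". Two further tables bring in time, both through the same three periods. One is by modal dose: "TEAEs by SOC/PT will be presented by modal dose within period (titration/dose response, maintenance, and taper period"). The other is by current dose: "TEAEs by SOC/PT will be presented by dose the subject was on at time of event within period". SAP 10.2 adds serious TEAEs and TEAEs leading to discontinuation or interruption, with no time split.

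On denominators, SAP 7.1.2 assigns the Safety Population to every safety analysis. SAP 11.2 allows, but does not require, a column N per treatment or dosing category. Neither section gives an N per period or for subjects still on drug. By contrast, SAP 8.1 does state the denominator for the disposition table.

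Other safety data are resolved in time. Laboratory tests, vital signs, ECG and the urinary symptom questionnaire are summarised at each time point (SAP 10.3, 10.4, 10.6). SAP 8.6 tabulates days at each dose level, but nothing links those days to AE counts.

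**The concern.** An extension study of about a year is run to learn what longer exposure adds. For AEs that means asking whether new events appear late, whether early events settle, and how many subjects were under observation when they did. In every planned AE table, an event starting in week 3 of maintenance falls in the same cell as one starting in month 11.

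The denominator adds to this. Subjects leave for relapse, persistent intolerability, poor compliance or new anti-spasticity treatment (Protocol 7.4, 7.7, 12.4), and Protocol 12.4 says they are not replaced. If late events are divided by everyone who started, subjects who were no longer exposed count as exposed without an event. A late risk then looks smaller than it was, and an absence of late events looks more reassuring than it should. This affects the Overall column as much as the dose columns.

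**Working it through.** The plan gives no calculated figure on this point. The sample size of about 300 is stated to have no statistical rationale (Protocol 11.3, SAP 6), so there is nothing to reproduce. The checks below are arithmetic on stated quantities, with the assumptions marked.

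**1. Share of dosing time in the undivided block.** Inputs from SAP 5.1: titration 9 days, maintenance 52 × 7 = 364 days, taper 14 days.
- Total: 9 + 364 + 14 = 387 days.
- Maintenance: 364/387 = 94.1%. Titration: 9/387 = 2.3%. Taper: 14/387 = 3.6%.

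The three-period split therefore puts almost all long-term exposure in one cell.

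**2. What one block hides.** Assume 300 subjects are at risk in the first half of maintenance and 240 in the second, with no subject counted in both halves. Block percentage = (early risk × 300 + late risk × 240)/300.
- Risk rising from 2% to 5%: (6 + 12)/300 = 6.0%.
- Risk falling from 5% to 2%: (15 + 4.8)/300 = 6.6%.

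Opposite time courses give nearly the same entry.

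**3. Late risk read against all starters.** Reading = true late risk × R/300, where R is the number still on drug. Assumed true late risk: 5%. Retention is also assumed, because the documents give no dropout rate.

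| Still on drug (R) | Retention | Cases (5% × R) | Reading over 300 |
|---|---|---|---|
| 270 | 90% | 13.5 | 4.5% |
| 240 | 80% | 12 | 4.0% |
| 180 | 60% | 9 | 3.0% |
| 150 | 50% | 7.5 | 2.5% |
| 100 | 33% | 5 | 1.7% |

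The last row uses the minimum in Protocol 5: "approximately 300 subjects are to be enrolled in order to achieve treatment of at least 100 subjects for 6 months". That is a floor for exposure and not a forecast of retention. With R as the denominator, every row would read 5%.

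**4. Zero late cases.** The exact two-sided 95% upper limit with no events is 1 − 0.025^(1/n).
- n = 300: 1.2%.
- n = 240: 1.5%.
- n = 150: 2.4%.
- n = 100: 3.6%.

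The plan specifies no confidence limits. These values show how far the reassurance from a zero count depends on the number at risk.

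**The case against.** The strongest reply is that the objective asks for an evaluation of long-term safety and does not ask how risk varies over time. The plan delivers a good deal:
- TEAE incidence over about a year by severity, relationship, dose and period;
- serious TEAEs and deaths with narratives;
- TEAEs leading to discontinuation or interruption;
- days at each dose;
- other safety measures at each time point.

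Every TEAE is listed by subject, so timing is not lost from the data. SAP 10.6 also allows further safety analyses after the fact. All of this stands. A reader might infer that the primary question goes unanswered, and the documents do not support that. Even so, listings and narratives are not an incidence analysis, and an analysis chosen after the results are seen carries less weight than a planned one.

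A reader might also infer that the SAP fixes all starters as the denominator throughout. It does not: SAP 7.1.2 points that way, but no denominator is written for the period or dose-at-event tables. Limiting the maintenance table to subjects who entered maintenance would fit the text. It would remove titration dropouts but not those who leave during the 52 weeks.

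The size of any understatement is also open. No planned table shows a late-period percentage, no dropout rate is given, and Protocol 5 lets the sponsor end the study once enough subjects have enrolled to meet the exposure requirement, so 300 may not be the final number.

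**Conclusion.** The point holds as a gap in the AE analysis. No AE table divides the 94% of planned dosing time spent in maintenance. No onset-interval, time-to-onset or person-time summary is planned, and no denominator is tied to subjects still on drug. The tables will give overall incidence for about a year of treatment. They will not show whether risk changes over that year.

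The effect on a late risk read against all starters is modest if retention is high (5% reads as 4.0% to 4.5% at 80% to 90%) and large if it is low (2.5% at 50%, 1.7% at the 6-month minimum). These readings assume a 5% late risk, 300 starters and the full Safety Population as denominator; they are illustrations and not predictions. A reader might go further and divide the 50-subject target by 300 to claim a sixfold understatement. That does not follow, because the 50 is a minimum for 80 mg/day for one year and says nothing about how many remain on drug at all doses.

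The change is cheap and worth making before database lock.

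**What to change.** Add to SAP 10.1 a summary of TEAEs and serious TEAEs by onset interval:
- Keep titration and taper as separate intervals. Split maintenance at scheduled visits, for example end of titration to Week 14, Weeks 14–28, 28–42 and 42–54.
- Use as denominator the number of subjects on drug at the start of each interval, and print it in the column header.
- Report first-onset incidence with exact 95% confidence intervals.
- Add exposure-adjusted rates per person-time, overall and by dose at onset, using the days at each dose level already planned in SAP 8.6.
- State the denominator for the existing period and dose-at-event tables.

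The AE onset dates and dosing dates needed are already collected, and the SAP revision history shows that AE tables by period and exposure days have been added before. The cost is SAP wording and some programming. Late intervals will rest on fewer subjects and be imprecise, which the confidence intervals will show.
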